7.6.3 Laboratory Data

Safety summaries based on laboratory test results include evaluation of laboratory abnormalities and changes in laboratory test values from baseline (baseline addressed further in [Section 8.2](#)). For summaries of the double-blind period, laboratory data obtained during treatment or up to 56 days after last injection of study medication in the double-blind period but no later than the start of the open-label period dosing will be eligible for analyses.

Laboratory abnormalities are identified using a pre-defined set of marked abnormality (MA) criteria (listed in Safety Data Convention). The frequency of subjects with laboratory MAs during the double-blind period based on pre-specified criteria will be tabulated by treatment group, for each analyte.

Laboratory measurements and their changes from baseline will be summarized by nominal visit and treatment group, for protocol specified analytes. Subjects who have laboratory measures at baseline and corresponding measures on at least one scheduled visit following administration of study drug will be included in the laboratory analyte assessment. Note that not all subjects have laboratory determinations for all analytes at all visits, and therefore the sample size may vary from analyte to analyte at each time point.

In addition shift tables for the following laboratory tests will be provided. The categorical classifications of these tests will be determined based on the cut points specified below and cross-tabulation of classification between baseline and each of the scheduled visits will be presented by treatment groups.

Table 7.6.3-1: Definitions of Analyte Cut Points

Analyte (Test Code)	Cut Points
Platelet Count (PLAT)	< 100x10 ⁹ c/L ≥ 100 x10 ⁹ c/L
Alanine Aminotransferase (ALT)	< 3xULN 3 - ≤ 5xULN > 5xULN
Aspartate Aminotransferase (AST)	< 3xULN 3 - ≤ 5xULN > 5xULN
Neutrophils (absolute)	< 0.5x10 ⁹ c/L 0.5 - ≤ 15x10 ⁹ c/L > 15x10 ⁹ c/L
G-Glutamyl Transferase (GGT)	< 3xULN 3 - ≤ 5xULN > 5xULN

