#### **5.3.5.1 Hematology Panel**

- Hemoglobin
- Total WBC count, including differential
- Platelet count

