**monocytes (%)** -  $> 2 \times \text{ULN}$ ;  $> 2 \times$  pretreatment if pretreatment above ULN

**neutrophil count (neutrophils+bands)** -  $< 0.67 \times$  pretreatment if pretreatment  $< 1000/\text{mm}^3$ ; otherwise,  $< 1000/\text{mm}^3$ .

**phosphate** -  $< 0.75 \times \text{LLN}$  or  $> 1.25 \times \text{ULN}$ ;  $< 0.67 \times$  pretreatment value if below LLN pretreatment, or  $> 1.33 \times$  pretreatment if above ULN pretreatment;  $> \text{ULN}$  if  $< \text{LLN}$  pretreatment, or  $< \text{LLN}$  if  $> \text{ULN}$  pretreatment

**platelet count** -  $< 0.67 \times \text{LLN}$  or  $> 1.5 \times \text{ULN}$ ; if below normal pretreatment,  $< 0.5 \times$  pretreatment value and  $< 100,000/\text{mm}^3$

**potassium** -  $< 0.9 \times \text{LLN}$  or  $> 1.1 \times \text{ULN}$ ;  $< 0.9 \times$  pretreatment if pretreatment below LLN, or  $> 1.1 \times$  pretreatment if pretreatment above ULN;  $> \text{ULN}$  if  $< \text{LLN}$  pretreatment, or  $< \text{LLN}$  if  $> \text{ULN}$  pretreatment

**protein, total** -  $< 0.9 \times \text{LLN}$  or  $> 1.1 \times \text{ULN}$ ;  $< 0.9 \times$  pretreatment if below LLN pretreatment, or  $> 1.1 \times \text{ULN}$  if above ULN pretreatment;  $> \text{ULN}$  if  $< \text{LLN}$  pretreatment, or  $< \text{LLN}$  if  $> \text{ULN}$  pretreatment

**SGOT and SGPT (ASAT and ALAT)** -  $> 3 \times$  upper limit of normal; if pretreatment above ULN,  $> 4 \times$  pretreatment value

**sodium** -  $< 0.95 \times \text{LLN}$  or  $> 1.05 \times \text{ULN}$ ;  $< 0.95 \times$  pretreatment if below LLN pretreatment,  $> 1.05 \times$  pretreatment if above ULN pretreatment;  $> \text{ULN}$  if  $< \text{LLN}$  pretreatment, or  $< \text{LLN}$  if  $> \text{ULN}$  pretreatment

**uric acid** -  $> 1.5 \times \text{ULN}$ ; if pretreatment above ULN,  $> 2 \times$  pretreatment value

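### The neutrophil shift table in SAP Table 7.6.3-1 has no boundary between 0.5 and 15 x10^9/L, so it does not show falls from within that range to between 0.5 and 1.0, below the protocol's own reporting limit.

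*SAP*

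**What the plan says.** SAP 7.6.3 (Laboratory Data) states that "shift tables for the following laboratory tests will be provided", naming platelets, ALT, AST, absolute neutrophils and GGT. On how classes are assigned it says: "The categorical classifications of these tests will be determined based on the cut points specified below". On layout it says: "cross-tabulation of classification between baseline and each of the scheduled visits will be presented by treatment groups". The neutrophil row of Table 7.6.3-1 reads "< 0.5x10 ⁹ c/L 0.5 - ≤ 15x10 ⁹ c/L > 15x10 ⁹ c/L". No other neutrophil boundary for the shift table appears in the SAP.

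The same section plans two other laboratory displays. One is a frequency table of marked abnormalities: "Laboratory abnormalities are identified using a pre-defined set of marked abnormality (MA) criteria (listed in Safety Data Convention"; that convention is not part of the documents. The other is continuous: "Laboratory measurements and their changes from baseline will be summarized by nominal visit and treatment group".

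Protocol Appendix 2 (Laboratory Guidelines) has an entry for "neutrophil count (neutrophils+bands"). It gives two criteria. If the pretreatment count is below 1000/mm3, the criterion is a value below 0.67 times pretreatment. Otherwise it is a value below 1000/mm3. The data for either display are collected: the hematology panel in Protocol 5.3.5.1 includes "Total WBC count, including differential", and Protocol Table 5.1-2 schedules that panel on Day 1 and at all six later double-blind visits.

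**The concern.** A shift table shows a change only when a subject crosses a class boundary. With boundaries at 0.5 and 15 x10^9/L, the middle class holds ordinary counts together with counts that the protocol itself treats as worth considering for an adverse event form. A table with nearly everyone in the middle-to-middle cell could then be read as evidence of no neutrophil effect, when it shows only that few subjects went below 0.5 or above 15.

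The display has some importance here. Neutrophils are one of only five tests chosen for shift tables. The permitted background treatments include methotrexate, azathioprine and mycophenolate (Protocol 3.3.1). The laboratory exclusions in Protocol 3.3.2 set a floor for total white cells (3,000/mm3) but none for neutrophils, so the baseline class carries information that eligibility does not fix.

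**Working it through.** **Inputs**
- Shift classes (SAP Table 7.6.3-1), in 10^9/L: < 0.5; 0.5 to ≤ 15; > 15.
- Appendix 2 limit for a pretreatment count of at least 1000/mm3: below 1000/mm3. Conversion: 1000 per mm3 x 10^6 mm3 per L = 1.0 x10^9/L.
- Baselines of 2, 4 and 7 x10^9/L. These are assumptions for illustration; the documents give no neutrophil distribution or normal range.

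**Width of the middle class.** 15 / 0.5 = 30-fold. The limit of 1.0 lies inside it.

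**Worked case.** Baseline 4.0, later value 0.6. Change = 0.6 - 4.0 = -3.4. Relative fall = 3.4 / 4.0 = 85%. Appendix 2: 0.6 < 1.0, so the limit is met. SAP class: middle at baseline, middle at the visit, so no shift.

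**Range of later values.** The results are the same for all three baselines. The last two columns show the effect of adding a boundary at 1.0, and of reading 15 as 1.5 (classes < 0.5, 0.5 to ≤ 1.5, > 1.5).

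| Later value | Meets Appendix 2 limit | Shift as written | Shift with 1.0 added | Shift if 15 means 1.5 |
|---|---|---|---|---|
| 0.4 | yes | yes | yes | yes |
| 0.5, 0.6, 0.9 | yes | **no** | yes | yes |
| 1.0, 1.4 | no | no | no | yes |
| 14.9, 15 | no | no | no | no |
| 15.1 | no | yes | yes | no |

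The second row is the blind spot: later values from 0.5 to < 1.0 meet the protocol's limit and do not register. This holds for any baseline from 1.0 to 15. A subject starting above 15 would show a shift from the top class to the middle one. A subject starting below 1.0 falls under the relative criterion in Appendix 2 instead.

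Reading 15 as 1.5 would make these falls visible as shifts, but 0.6 and 1.4 would share a class. The number of subjects crossing 1.0 could still not be read from the table. The 1.0 boundary is therefore useful under either reading.

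**The case against.** The strongest reply is that the shift table is supplementary and the plan covers neutrophils in three other ways.

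- Marked abnormalities are tabulated by arm for each analyte.
- Values and changes from baseline are summarized by visit and arm, and SAP 7.1 includes minima and maxima among the standard statistics. A value of 0.6 that is the lowest in its arm would appear as the minimum, and the fall of 3.4 enters the change summary.
- Clinically significant laboratory results are recorded as adverse events (Protocol 6.3) and enter the adverse event summaries (SAP 7.6.1).

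This stands, and it limits the point. It does not remove it. The marked-abnormality limit for neutrophils is in a convention that cannot be checked here, a minimum does not count subjects, and mean changes can dilute a few individual falls.

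A second reply is that Appendix 2 guides investigators on what to put on the adverse event form, and nothing requires the SAP's classes to follow it. That is also correct, so the difference is a missed alignment and not a contradiction between the documents.

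A reader might go further in three ways that the documents do not support.

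- That the table cannot show any difference between arms, or misses almost every relevant fall. It is presented by arm and registers values below 0.5 and above 15. The documented gap against the protocol's limit is 0.5 to < 1.0.
- That the neutrophil row is the odd one out because the other rows separate normal from abnormal. The lowest ALT, AST and GGT class is everything below 3 times ULN, which pools normal results with raised ones.
- That 15 is 1.5 with the decimal point lost. This is possible, but 15 appears twice and the decimal in 0.5 survives in the same row. A low/middle/high layout for extreme values is also coherent.

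**Conclusion.** The point holds in a limited form. As written, the neutrophil shift table does not show a fall from a baseline of 1.0 to 15 x10^9/L to a value from 0.5 to < 1.0, although such a value meets the Appendix 2 reporting limit. The loss is one specific quantity: the number of subjects, by visit and by arm, who cross the protocol's low limit.

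The class assignment follows directly from the printed cut points and needs no distributional assumption. How many subjects would be affected cannot be estimated from the documents. How much the marked-abnormality table compensates cannot be judged without its criteria. The documents define no grades of neutropenia or neutrophilia, and the conclusion relies on none, only on the 1.0 limit. The effect is on descriptive safety reporting; the primary and secondary efficacy analyses are untouched.

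**What to change.** Confirm whether 15 is the intended upper cut point, and add a class boundary at 1.0 x10^9/L to the neutrophil row of Table 7.6.3-1. One version that keeps the existing cut points is < 0.5, 0.5 to < 1.0, 1.0 to ≤ 15 and > 15 x10^9/L. Any further boundary, such as 1.5, is for the sponsor to decide, because neither document sets one for neutrophils.

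The cost is one row of one SAP table and the matching output shell. No new data are needed, since the differential count is already collected at every double-blind visit. These are display categories only and alter no clinical rule.

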7.6.4 Vital Signs

- Summary statistics for vital sign measurements (systolic BP, diastolic BP, heart rate and body temperature) will be presented at study baseline, and prior and after injection by scheduled visit and treatment group.

Anti-nuclear antibody (ANA) status will be categorized as negative and positive that correspond

[REDACTED]

[REDACTED]

[REDACTED]

[REDACTED]

[REDACTED]

[REDACTED]

[REDACTED]

[REDACTED]

[REDACTED]

[REDACTED]

[REDACTED]

[REDACTED]

[REDACTED]

7.8 Additional Analyses to be Included in 24 Week CSR

In addition to safety summaries specified above for the 24-week double-blind period; summaries of all AEs, AEs of special interest (SAEs, Malignancies, Myositis related AEs and autoimmune events) reported in the database up to the 24-week database lock will be included in the 24-week study report. These AEs will be presented by the double-blind treatment groups for the cumulative abatacept period based on the as-treated analysis population.

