### **8.4.7 Week 52 Analysis**

The final study (Week 52 analysis) for all study sites will be performed when all subjects have completed a total of 52 weeks on treatment in the study (ie. completed the Open-Label Period) and/or the follow-up period of the study. The Week 52 analysis will include efficacy and safety

analyses. No formal statistical testing will be conducted for any of the efficacy analyses included in the final Week 52 analysis, appropriate summary statistics will be provided. Safety summaries will include events reported from the start of the Open-Label Period up to 56 days post last dose date in the Open-Label Period. Cumulative abatacept safety summaries will also be provided for all subjects who received abatacept at any time during the study. The cumulative safety summaries will include all AEs reported from the first dose date of abatacept up to 56 days post the last dose date of abatacept in the study.

The Week 52 analyses will be based on open-label treated analysis population except for the cumulative abatacept safety summaries which will be based all subjects who received at least one dose of abatacept at any time during the study.

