The cumulative abatacept period: starts at the first dose date/time of abatacept and lasts until the last dose date of abatacept in the study + 56 days. For subjects randomized to placebo in the double-blind period the first dose date of abatacept will be the first dose date in the open-label period.

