6.3 Populations for Analyses

Efficacy endpoints will be summarized according to the Intent-to-Treat (ITT) population and safety endpoints will be summarized according to the as-treated analysis population. These populations are described briefly below along with other populations.

- **Intent-to-Treat Analysis Population:**

The Intent-to-Treat (ITT) analysis Population is defined to include all subjects randomized into the study for whom Case Report Form (CRF) data indicate that at least one dose of study medication (abatacept or placebo) is administered during the double-blind period.

All subjects who are randomized but never received study medication are to be excluded. Given the blinded nature of this study, it is reasonable to assume that subjects who discontinue prior to the receipt of study medication do so for reasons unrelated to study medication. Subjects are grouped according to the treatments to which they are randomized by IXRS.

ITT analysis population is also referred to as “All Randomized and Treated Subjects”.

- **As-Treated Analysis Population:**

The As-Treated analysis population contains all subjects for whom CRF data indicate that at least one dose of study medication was administered during double-blind period.

Subjects are grouped according to the treatments to which they are randomized, except in cases where information is available, which indicates that a subject receives a different treatment for the entire course of double-blind period. In this case, the subject will be presented by the treatment they actually received.

The As-Treated analysis population will also be referred as “All Treated Subjects”.

- **Per-Protocol Analysis Population:**

The Per-Protocol analysis population is defined as a subset of the ITT analysis population which excludes subjects who have relevant protocol deviations during the double-blind study period. Relevant protocol deviations are those protocol deviations that might affect the primary efficacy endpoint of the study. A programmable list of relevant protocol deviation criteria is included in [APPENDIX 1](#).

The analysis of the primary efficacy endpoint will be repeated in the Per-Protocol analysis population. The Per-Protocol analysis population will exclude subjects with at least 1 relevant protocol deviation.

- **Open-Label Treated Analysis Population:**

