7.3.1 Subject Disposition

The disposition of subjects in the double-blind period will be presented as follows:

- Number of subjects enrolled at screening.
- Number of subjects randomized.
- Number of subjects treated in the double-blind period (i.e. who received at least 1 dose of study drug (abatacept or placebo).
- Number of subjects who discontinued during the double-blind period, together with reasons for discontinuation (taken from the eCRF status page).
- Number of subjects who completed the double-blind period, but who did not enter the open-label period and reason for not entering the open-label period (taken from the eCRF status page).

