11.7 Safety

Unless otherwise specified, the same safety analyses for the Week 24 analysis will be performed for AEs that occurred during the open-label / open-label extension / long-term extension periods.

Additional analyses will also be provided for the cumulative Abatacept period in subjects who received at least one dose of Abatacept at any time during the study. The analyses in addition to the safety analyses for Week 24 analysis described in [Section 7.6](#) are explicitly summarized in the following:

- Incidence rates by 3-month intervals for SAEs, pre-specified infections and adverse events of interest (*Infections, Malignancy, Autoimmune disorders*) will be provided for cumulative abatacept period.
- Multiple events will be reported based on unique AEs for each specific preferred term. For each subject and preferred term, a single record (unique AE) is used to represent multiple AEs when:
 - Multiple AE records have the same onset date.
 - The onset date of an event record is either the same day or 1 day later than the resolution date of a preceding event record (continuous events).
 - The onset date of an event record is after the onset date and prior to or on the resolution date of a preceding event record (overlapping events).

The unique AE record contains the earliest onset date, latest resolution date (if available), highest intensity, latest relationship, the most severe adverse event type (i.e., the SAE if ever reported as SAE), treatment required (will be yes if ever required) and highest action taken in the following order (highest to lowest): drug discontinued, drug interrupted, dose reduced, dose increase, none.

Multiple events will be presented for the cumulative abatacept period based on subjects who received at least one dose of abatacept at any time during the study.

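### SAP 7.8 puts the Week 24 cumulative abatacept tables on the as-treated population, so placebo-randomised subjects who never received abatacept can dilute the placebo-randomised column

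*SAP*

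**What the plan says.** SAP 7.8 covers all adverse events and selected events of special interest in the database up to the Week 24 lock. It splits them by double-blind arm and defines the tables as being "for the cumulative abatacept period based on the as-treated analysis population".

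Two definitions in SAP section 6 decide what this means:

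- **Population (SAP 6.3).** The as-treated population "contains all subjects for whom CRF data indicate that at least one dose of study medication was administered during double-blind period". Study medication here is abatacept or placebo, so one placebo injection is enough.
- **Period (SAP 6.1).** This window "starts at the first dose date/time of abatacept and lasts until the last dose date of abatacept in the study + 56 days". In the placebo arm, "the first dose date of abatacept will be the first dose date in the open-label period".

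For later reports the population is different. Protocol 8.4.7 bases the cumulative safety summaries at Week 52 on "all subjects who received at least one dose of abatacept at any time during the study", as an express exception to the default population for that analysis. Protocol 8.4.9 does the same for the long-term extension. SAP 11.7 describes analyses for the "cumulative Abatacept period in subjects who received at least one dose of Abatacept at any time during the study", and SAP section 7 ties the cumulative period in the final analysis to abatacept-treated subjects.

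One rule points the other way. Protocol 8.4.3 assigns all Week 24 safety analyses to the as-treated population, and SAP 6.3 assigns safety endpoints to it in general.

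**The concern.** The period and the population in 7.8 do not match. A placebo-randomised subject who stops before the open-label period, or completes Week 24 and does not go on, has no cumulative abatacept period. Such a subject can add nothing to the numerator but, read literally, counts in the denominator.

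These subjects are foreseeable. Protocol 3.1.5 requires discontinuation for worsening that needs a change of therapy before Week 12, and for failed rescue. Protocol 3.5 adds missed-dose rules. SAP 7.3.1 plans a disposition row for the "Number of subjects who discontinued during the double-blind period, together with reasons for discontinuation", and another for completers who do not enter the open-label period.

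At stake are the percentages with serious, malignant and autoimmune events on abatacept in the first study report. In the placebo-randomised column they could look lower than they are among subjects actually exposed. The same named period would also rest on one population at Week 24 and another from Week 52 onward.

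**Working it through.** **The plan's own figure.** The documents give no figure for these tables. The only planned number used is 75 subjects per group (Protocol 8.1, SAP 5). It comes with a stated power of about 90% for 60% versus 33%, two-sided 5%, continuity-corrected chi-squared test. Check with n = 75 and mean rate 0.465:

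- se0 = √(0.465 × 0.535 × 2/75) = 0.0814
- se1 = √((0.60 × 0.40 + 0.33 × 0.67)/75) = 0.0784
- power = Φ((0.27 − 1/75 − 1.96 × 0.0814)/0.0784) = 89.2%

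This agrees with the stated figure. It confirms the planned size only and has no bearing on the safety denominator.

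**Inputs for the dilution**

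- Placebo-randomised subjects in the as-treated population: 75, assuming that all planned subjects are dosed.
- k: placebo-randomised subjects who never receive abatacept. This is not in the documents and is assumed to lie between 0 and 15. SAP 7.5.3.2 uses 7 missing responses to illustrate the tipping-point analysis. That is not a count of never-exposed subjects, so k = 7 below is only an illustration.
- Denominator: the as-treated N.

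**Formula.** If x of the 75 − k exposed subjects have an event, the percentage among the exposed is x/(75 − k), and the table shows x/75. The ratio of shown to exposed is (75 − k)/75, and the relative understatement is k/75.

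| k (assumed) | Factor | Relative understatement | True 10% shown as | True 30% shown as |
|---|---|---|---|---|
| 0 | 1.000 | 0% | 10.0% | 30.0% |
| 5 | 0.933 | 6.7% | 9.3% | 28.0% |
| 7 | 0.907 | 9.3% | 9.1% | 27.2% |
| 10 | 0.867 | 13.3% | 8.7% | 26.0% |
| 15 | 0.800 | 20.0% | 8.0% | 24.0% |

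**Abatacept column.** Apart from dosing errors, every as-treated subject in this column has had abatacept in the double-blind period and so has a cumulative period. The factor is 1.000 for every k.

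**Counts and person-year rates.** Never-exposed subjects add no events and no abatacept exposure, so neither changes.

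**Pooled column.** SAP 7.8 mentions none. If one were produced, with equal event rates in both groups, its factor would be (150 − k)/150, which is 0.900 at k = 15.

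**The case against.** The strongest defence is that 7.8 follows the rule written for this report: Protocol 8.4.3 puts all Week 24 safety analyses on the as-treated population. A reader might infer that the documents use abatacept-exposed subjects everywhere except 7.8, and they do not support that. The exposed-subject rule is written for the Week 52 and later analyses, and 7.8 sits between that rule and the general Week 24 rule. This part of the defence stands, and the fix has to acknowledge it. It does not remove the mismatch, because 8.4.3 describes double-blind summaries, where every as-treated subject has a period at risk.

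Second, 7.8 never states a denominator. Number and percent of subjects is specified for the adverse event tables in SAP 7.6.1. Naming the cumulative period could be read as already limiting the table to subjects who have one, with as-treated serving only as the grouping rule. That reading is possible, so the dilution is conditional. Two programmers could still produce different tables from the same text.

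Third, the absolute effect is small. One malignancy is 1.33% as 1/75, 1.43% as 1/70 and 1.54% as 1/65. The controlled double-blind comparison in SAP 7.6, including the risk differences in 7.6.2, is untouched. Both statements are correct and limit the importance of the point.

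Finally, a reader might infer that 7.8 is also deficient because it shows arms with unequal abatacept exposure without exposure-adjusted rates. The documents do not make that an error. Columns by original arm already separate the longer from the shorter exposure, SAP 11.7 plans rates per 100 person-years for the cumulative period, and the opening of SAP 7.6 is redacted, so nothing can be said to be absent from it.

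**Conclusion.** The point holds in a limited form. The population named in 7.8 can include placebo-randomised subjects who have no cumulative abatacept period, and it differs from the population for later cumulative summaries. On a literal reading, the placebo-randomised column is understated by a relative k/75, which is 0% to 20% for k from 0 to 15. This rests on three assumptions: 75 dosed placebo subjects, an assumed k, and the as-treated N as denominator.

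A reader might infer that all event percentages in these tables are understated, or that the whole placebo arm dilutes them. Neither follows. The abatacept column does not change, placebo subjects who go on to open-label abatacept are correctly included, and there is no dilution if k = 0. The primary endpoint and the double-blind safety comparison are not involved. The change is worth making because the tables are pre-specified safety output and any error would run towards lower apparent risk.

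**What to change.** In SAP 7.8, replace the as-treated population with subjects who have had one or more doses of abatacept by the data cutoff, still presented by double-blind treatment group. Add a sentence noting that this departs from the as-treated rule for Week 24 safety analyses in Protocol 8.4.3 and matches Protocol 8.4.7 and 8.4.9 and SAP 11.7.

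The cost is one phrase and one cross-reference. No new data are needed, since dose dates already define the period. Percentages in the placebo-randomised column will be the same or somewhat higher.

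Exposure-adjusted rates at Week 24 are optional and a larger change. SAP 11.5.1.4 computes cumulative abatacept exposure only at study closeout, so it would need amending, together with a rule for cumulative exposure in subjects still on treatment at the cutoff.
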